## STUDY SUMMARY

Title	Myocardial Protecting Role of Glutamine in Patients with Low Ejection Fraction Undergoing Elective On-Pump Coronary Artery Bypass Graft Surgery
Methodology	Randomized, double blinded, controlled study
Study Duration	Estimated duration for the main protocol (e.g. from start of screening to last subject processed and finishing the study) is approximately 1 year
Study Center	National Cardiovascular Center Harapan Kita, West Jakarta, Jakarta, Indonesia
Objectives	
Primary Objective: To determine whether intravenous glutamine could mitigate the negative impact of on-pump CABG procedures and provide better clinical outcome in patients undergoing coronary artery bypass graft surgery under cardiopulmonary bypass.
 
Secondary Objective: To determine whether intravenous glutamine could prevent the decline of plasma glutamine level, reduce myocardial damage, improve hemodynamic profile, and reduce morbidity low ejection fraction patients undergoing coronary artery bypass graft surgery under cardiopulmonary bypass.

Number of Subjects	60 randomized patients divided into two groups; Glutamine and Control
Diagnosis and Main Inclusion Criteria	
Inclusion Criteria
 

– Male and female patients, aged <math>\geq</math> 18 years old with coronary heart disease indicated for elective coronary artery bypass grafting under cardiopulmonary bypass

– Left ventricle ejection fraction of 31-50%, confirmed by echocardiography or radionuclide imaging

– No history of heart surgery

– Agree to participate in the study and signed a written informed consent

	
Exclusion Criteria
 

– Change of surgical plan from elective into emergency CABG surgery

– Additional procedures other than coronary artery bypass graft procedure

– Onset of myocardial infarction within the last three months

– Blood creatinine level > 2 mg/dL

– ALT/AST level > 1.5x of normal value

– Use of preoperative intra-aortic balloon pump

– History of stroke with onset of less than 3 months

– Preoperative atrial fibrillation

– Heart conduction problem or pacemaker use

– Contraindications to pulmonary artery catheter insertion

 
Drop out criteria
 

– Stroke after surgery

– Perioperative myocardial infarction based on type 5 myocardial infarct criteria

– Haemorrhage complications requiring repeat surgery

– Use of continuous veno-venous hemofiltration or haemodialysis after coronary artery bypass graft surgery

– Delayed sternal closure

– Aortic cross-clamp duration of > 120 minutes and/or cardiopulmonary bypass duration of >180 minutes

Study Product, Dose, Route, Regimen	

– Glutamine Group: will receive intravenous infusion of 0.5 mg/kgbw L-alanyl-L-glutamine dipeptide (Dipeptiven, Fresenius Kabi, Bad Homburg, Germany) diluted in normal saline up to 500 mL, started after induction of anesthesia for 24 hours.

	

– Control Group: will receive intravenous infusion of 500 mL normal saline, started after induction of anesthesia for 24 hours

Statistical Methodology	
Primary Endpoint
 
Plasma glutamine before induction to anesthesia and 24 hours after CPB, and plasma troponin I before induction to anesthesia, 5 minutes, 6 hours, 24 hours and 48 hours after CPB.
 
Secondary Endpoint
 
Alpha-Ketoglutarate, myocardial injury score, apoptosis index, anti-cardiac troponin I expression, ejection fraction, cardiac index, plasma lactate, intensive care unit ventilation time, intensive care unit length of stay and vasoactive inotropic score.

**Purpose:**

The primary objective is to determine whether intravenous glutamine could prevent the decline of plasma glutamine level, reduce myocardial damage, improve hemodynamic profile, and reduce morbidity low ejection fraction patients undergoing coronary artery bypass graft surgery under cardiopulmonary bypass.

**Background:**

Coronary artery disease has the highest mortality rate worldwide and coronary artery bypass grafting (CABG) is the most common cardiac surgery performed in patients with coronary artery disease to revascularize the heart. Despite improvement in operation techniques, cardioplegia, cardiopulmonary bypass, myocardial injury related to on-pump CABG is still prominent. In patient with low ejection fraction (EF) undergoing on-pump CABG, myocardial injury is related to worse outcome and prognosis during peri-operative and postoperative period. On-pump CABG patients with low ejection fraction has increased (up to four times higher) postoperative in hospital mortality rate compared to patient with normal ejection fraction. Administration

of intravenous glutamine had been documented in reducing myocardial damage during cardiac surgery and previous studies indicated that glutamine can protect against myocardial injury by various mechanism during ischemia and reperfusion.

### **Goals of the study:**

To analyze the effect of intravenous glutamine in low EF patients undergoing on-pump CABG surgery in:

1. Reducing myocardial damage by a decrease of myocardial injury score, apoptotic index and increase of anti-cardiac troponin I expression through right atrial appendage tissue sample, as well as decrease of troponin I level.
2. Improving myocardial metabolism by a decrease in plasma lactate levels, increase of plasma glutamine levels and alpha ketoglutarate ( $\alpha$ -KG) levels in the right atrial appendage tissue sample.
3. Improving hemodynamic profile through an increase in EF and cardiac index after CPB
4. Reducing postoperative morbidity by the decrease of ventilator duration, duration of intensive care, and use of postoperative vasoactive and inotropes

### **Duration of the Study:**

The study is estimated to complete within 2 years from study initiation.

### **Potential Benefits and Risks:**

Every effort is taken during the study period to maximize patient safety. To fulfil this goal, the study staff employs stringent procedures to reduce the risk of adverse events during the study period. The result of this study can be applied in clinical practice to ascertain the benefits of glutamine as a myocardial protector to reduce perioperative risks and treatment costs of elective on-pump CABG for patients with low EF.

## **Methods:**

### *Study Design*

This is a double-blind, randomized controlled trial involving sixty (60) subjects undergoing elective on-pump coronary artery bypass graft will be randomized into two groups.

### *Study Population and Selection Criteria*

All participants will be required to sign a written informed consent, be willing and able to comply with all study requirements and should meet the following criteria:

- Male and female patients, aged  $\geq$  18 years old with coronary heart disease indicated for elective coronary artery bypass grafting under cardiopulmonary bypass
- Left ventricle ejection fraction of 31-50%, confirmed by echocardiography or radionuclide imaging
- No history of heart surgery
- Agree to participate in the study and signed a written informed consent

Subjects will be **excluded** from the study based on the following criteria:

- Change of surgical plan from elective into emergency CABG surgery
- Additional procedures other than coronary artery bypass graft procedure
- Onset of myocardial infarction within the last three months
- Blood creatinine level  $> 2$  mg/dL
- ALT/AST level  $> 1.5x$  of normal value
- Use of preoperative intra-aortic balloon pump
- History of stroke with onset of less than 3 months
- Preoperative atrial fibrillation
- Heart conduction problem or pacemaker use
- Contraindications to pulmonary artery catheter insertion

### *Recruitment Methods*

All patients aged above 18 years old with coronary artery disease indicated for elective CABG surgery at the National Cardiovascular Center Harapan Kita are offered to be

a participant in this study. The primary investigator, [name] and his partners (co-investigators) will be performing the procedures accordingly for both control and treatment groups.

#### *Data Collection*

Data on sex, age, weight, height and preoperative EF are collected through direct history-taking and preoperative medical records. Data on CPB time, aortic cross-clamping time, number of distal coronary artery grafts are collected from surgery reports. Arterial blood sampling for troponin I levels measurement are collected: (1) before induction, (2) at 5 minutes, (3) at 6 hours, (4) at 24 hours, and (5) at 48 hours after CPB. Plasma troponin I is measured using the troponin I (human) ELISA kit (Abnova, KA0233) with colorimetry method. Arterial blood samples for plasma glutamine levels measurement are collected before induction and 24 hours after the CPB. Plasma glutamine levels is measured using the Sigma–Aldrich GLN1 glutamine/glutamate determination kit (Sigma–Aldrich, GLN1-1KT) using colorimetry method. To obtain plasma samples, blood is centrifuged for 15 minutes at a speed of 3500 X G within a maximum period of 30 minutes after collection and is stored at -80°C.

A 5×5 mm sample of the right atrial appendage tissue are collected at 5 minutes after CPB and are immediately transported to the laboratory at 4°C within 30 minutes of collection. The tissue sample is divided for  $\alpha$ -ketoglutarate ( $\alpha$ -KG) measurement and paraffin block preparation for histopathological examinations. A total of 20 mg of tissue is homogenized and centrifuged to obtain the supernatant. A protease inhibitor is added to the supernatant and then stored at -80°C until cellular  $\alpha$ -KG levels are examined. The examination of  $\alpha$ -KG is performed using  $\alpha$ -KG assay kit (Abcam, ab83431) with colorimetry method.

Myocardial injury score is measured on preparations stained with hematoxylin and eosin (H&E) with a scoring system from 0 to 3 as follows: 0 = no change; 1 = slight changes: focal myocyte damage or small multifocal degeneration with slight degree of inflammation; 2 = moderate changes: extensive myofibrillar degeneration and/or diffuse inflammatory process; 3 = severe changes: necrosis with diffuse inflammatory process. Terminal deoxynucleotidyl transferase-mediated deoxyuridine triphosphate nick end-labelling (TUNEL) staining is performed using the TUNEL assay kit (Abcam, ab206386). Cell nuclei with positive TUNEL staining is colored brown. The apoptotic

index is calculated based on the average number of cells with positive TUNEL staining. Expression of anti-cardiac troponin I is observed using anti-cardiac troponin I antibody (Abcam, ab47003). Measurement of anti-cardiac troponin I expression is performed on preparations stained with anti-cardiac troponin I antibody using a scoring system ranging from 0 to -3, as follows: 0 = no loss of staining; -1 = minimal decrease in staining, compared to normally stained tissue; -2 = clear decrease in staining with some positivity (brown color) remaining; -3 = no positive (brown color) staining. For quantitative analysis, histopathological examinations are made on as many as six fields of view per specimen under a light microscope (Olympus BX50, Tokyo, Japan) and photographed for further analysis. The histopathological specimens are assessed separately by two blinded examiners to get an average score.

Arterial blood samples for plasma lactate levels measurement are collected: (1) before induction, (2) at 5 minutes, (3) at 6 hours, (4) at 24 hours, and (5) at 48 hours after CPB. Lactate examination is performed using the Nova Biomedical Stat Profile® pHOX Ultra analyzer (Nova Biomedical, Waltham, MA, USA) with basic enzymatic method.

Ejection fraction measurements are taken: (1) after induction and (2) at 5 minutes after CPB, through TEE examination using the modified Simpson method. Cardiac index (CI) measurements are taken: (1) after induction, (2) at 5 minutes, (3) at 2 hours, (4) at 6 hours, and (5) at 24 hours after CPB. The values are obtained from calculating cardiac output (CO) per body surface area (in m^2). Cardiac output is measured via a pulmonary artery catheter using thermodilution method. The measurements are performed three times, averaged, and considered valid if the variation between the three values is less than 10%. Body surface area is calculated using the Mosteller formula. Morbidity variables consist of ventilator time, postoperative use of vasoactive and inotropic agents, and duration of intensive care are collected from the medical record. Vasoactive and inotropic score (VIS) is calculated (VIS = dopamine dose [μg kg min] + dobutamine [μg kg min] + 100 × epinephrine dose [μg kg min] + 10,000 × vasopressin [units kg min] + 100 × norepinephrine dose [μg kg min]) using the maximum dosing rates of vasoactive and inotropic medications (μg kg min or IU kg min) during the first 24 hours after postoperative ICU admission.

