## **STATISTICAL ANALYSIS PLAN**

### **RANDOMIZATION**

Subjects who meet all inclusion and exclusion criteria will be randomized into two groups, glutamine and control group. Subject allocation will be carried out through block randomization and known only by the pharmacist, and the confidentiality are maintained so that subjects, doctors/nurses, researchers, and data analysers does not know the allocation of each subject.

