**Post-Operative Vasoactive and Inotropes**

Parameters	1	4	6	8	12	18	24	36	48
Dobutamine (mcg/kg/minute)									
Epinephrine (mcg/kg/minute)									
Milrinon (mcg/kg/minute)									
Vasopressin (unit/kg/minute)									
Norepinephrine (mcg/kg/minute)									
VIS*									

\*VIS = dopamine dose (in mcg/kg/minute) + dobutamine dose (in mcg/kg/minute) + 100 x epinephrine dose (in mcg/kg/minute) + 10 x milrinone doses (in mcg/kg/minute) + 10.000 x vasopressin dose (in unit/kg/minute) + 100 x norepinephrine dose (in mcg/kg/minute)

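### The secondary endpoint VIS has two conflicting formulas: the Data Collection section omits milrinone, while the CRF adds 10 × milrinone and lacks a dopamine row and a field for the 24-hour maximum

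*Combined protocol and SAP*

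**What the plan says.** The score (VIS) is one of ten outcomes under Secondary Endpoint. It is the only score defined for the drug-support part of the fourth item in Goals of the study, which names "duration of intensive care, and use of postoperative vasoactive and inotropes".

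Two places define it.

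- **Data Collection.** The definition starts "Vasoactive and inotropic score (VIS) is calculated (VIS = dopamine dose" and sums dopamine, dobutamine, 100 × epinephrine, 10,000 × vasopressin and 100 × norepinephrine. It is calculated "using the maximum dosing rates of vasoactive and inotropic medications" "during the first 24 hours after postoperative ICU admission". The same section gives the source: "postoperative use of vasoactive and inotropic agents, and duration of intensive care are collected from the medical record".
- **CRF, Post-Operative Vasoactive and Inotropes.** The footnote has those five terms with the same weights and one more, in the stretch "10 x milrinone doses (in mcg/kg/minute) + 10.000 x vasopressin dose (in unit/kg/minute". The table has a row "Milrinon (mcg/kg/minute" alongside rows for dobutamine, epinephrine, vasopressin, norepinephrine and VIS. Its columns are 1, 4, 6, 8, 12, 18, 24, 36 and 48, each with its own VIS cell.

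**The concern.** An endpoint needs one scoring rule. Here there are two, and they disagree for every patient who receives milrinone in the scoring window. The Data Collection formula gives no weight to a drug that the trial's own form sets out to record, so support by milrinone alone looks the same as no support. That runs against the purpose of the endpoint, which is to measure how much support patients need. With two written formulas and no order of precedence, the choice could also be left until results are known.

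Two smaller problems concern data capture. Dopamine is in both formulas but has no row on the form. The definition rests on maximum rates over 24 hours, but the form offers only readings at fixed times. Someone scoring from the form alone would miss dopamine and any peak between readings, and might take the largest VIS cell instead of combining each drug's own maximum.

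**Working it through.** The plan states no expected value or SD for this score, so there is no figure to reproduce. The check compares the two definitions and applies both to the same rates. **All drug rates below are assumptions chosen for illustration**, in mcg/kg/min.

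**1. Terms and capture**

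| Drug | Weight, Data Collection | Weight, CRF footnote | Row on CRF |
|---|---|---|---|
| Dopamine | 1 | 1 | no |
| Dobutamine | 1 | 1 | yes |
| Epinephrine | 100 | 100 | yes |
| Milrinone | none | 10 | yes |
| Vasopressin | 10,000 | 10,000 | yes |
| Norepinephrine | 100 | 100 | yes |

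**2. Difference per patient**

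The five shared terms cancel: CRF score − Data Collection score = 10 × milrinone rate.

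- 10 × 0.25 = 2.5 points
- 10 × 0.50 = 5.0 points
- 10 × 0.75 = 7.5 points

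With dobutamine 5 and norepinephrine 0.05, the shared part is 5 + 100 × 0.05 = 10. The Data Collection score stays at 10 whatever the milrinone rate. The CRF score is 12.5, 15.0 or 17.5 at the three rates above.

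With milrinone alone at 0.5, the Data Collection score is 0 and the CRF score is 5.0.

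**3. Difference between arms**

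With non-users counted as 0, the difference in mean score (glutamine − control) changes by 10 × (mean milrinone maximum in the glutamine arm − mean milrinone maximum in the control arm). This is 0 if the two means are equal. Even then, the spread of the scores and the order of patients can change, which would matter for a test that uses either. The documents give no milrinone use, no SD for VIS and no test for this endpoint, so the calculation can go no further.

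**4. Missing dopamine row**

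Add dopamine at 5 to the shared part of 10. The score should be 15, but the CRF rows give 10.

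**5. Maximum rule**

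- Reading A: dobutamine 5, norepinephrine 0.02 → 5 + 100 × 0.02 = 7
- Reading B: dobutamine 2, norepinephrine 0.08 → 2 + 100 × 0.08 = 10
- Largest single-column score: 10
- Score from each drug's own maximum: 5 + 100 × 0.08 = 13

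The gap is 3 points. It is 0 if all drugs peak in the same column. The form does not state the unit of its columns; if they are hours, columns 36 and 48 fall outside the scoring window. Neither the Research Sample Outcomes page nor the CRF checklist supplies a field for the maximum.

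**The case against.** The formula conflict is hard to dispute, since both versions are printed as formulas in text. The case on the other side concerns how much it matters.

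- **The data can be recovered.** Data Collection draws drug use from the medical record, does not call for a CRF field for the maximum, and already reads most naturally as each drug's own maximum. No passage says that VIS will be scored from the CRF cells, and columns 1 to 24 would give an approximate maximum. This stands: the capture gaps matter only if the form is the sole source. The record cannot, however, settle which formula applies.
- **Analysts are blinded.** Randomization says that "data analysers does not know the allocation of each subject". A choice made while that holds cannot be steered toward an arm. This also stands, and it limits the risk to a choice deferred past unblinding. Nothing in the plan prevents such a deferral.
- **The drugs may be rarely used.** If dopamine is never given, the missing row has no numerical effect. The documents do not report use of either drug, but a dedicated milrinone row shows that milrinone was expected.
- **The CRF is an appendix.** One could argue that the protocol body takes precedence. No passage says so, and precedence would leave milrinone-only support scored as 0.
- **It is one of ten secondary endpoints.** This is true, and it is why the point does not rank higher.

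**Conclusion.** The concern holds. The two definitions of VIS conflict by one term, 10 × milrinone, and the plan does not resolve the conflict. The per-patient difference is exact: 1 point per 0.1 mcg/kg/min, or 2.5 to 7.5 points over the assumed range of 0.25 to 0.75. The effect between arms may be zero and cannot be estimated from the documents. Only patients who receive milrinone are affected.

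The missing dopamine row and the missing field for the maximum are secondary. They are recoverable from the medical record and cause error only if VIS is scored from the form alone. The formula conflict does not depend on how the CRF table is laid out; the missing dopamine row does, and is worth confirming on the printed form.

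This should be corrected, but it does not threaten the trial's main conclusion.

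**What to change.** Before unblinding:

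1. Reconcile Data Collection and the CRF footnote to one VIS formula that scores every drug the form records. Adding the CRF's milrinone term to Data Collection is the natural choice, because the form already collects the drug. It remains a choice for the sponsor to make and state, since nothing says that the CRF governs.
2. Add a dopamine row to the CRF table, and one maximum-rate entry per drug for the 24-hour window after ICU admission, filled from the medical record.
3. State that the analysed score is computed from those per-drug maxima. The drawback is that such a sum can combine rates that were not given at the same time, so the choice should be explicit.
4. Report the number of milrinone and dopamine users in each arm, so that readers can see how far the scoring rule matters.

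The cost is a short protocol amendment and a CRF edit: one extra row and one extra column, which makes six maximum-rate entries per patient. Under Institutional Review Board, the amendment needs approval before it takes effect. No new patient procedure is needed, because drug use is already taken from the medical record.

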### *Expected Outcomes*

It is the investigator's expectation that administration of intravenous glutamine will be beneficial as a myocardial protector in low EF patients undergoing on-pump CABG surgery.

### *Adverse Reactions*

There is no expectation of any adverse outcomes or reactions, should there be any adverse outcome or reactions, necessary management and will be taken in accordance with the standard medical protocol at the National Cardiovascular Center Harapan Kita Hospital. All participants will be given access to contact information of the primary investigator performing this study. Any adverse reactions will be reported immediately to the primary investigator or co-investigators.

### **Reasons for Withdrawal or Termination:**

A subject may be discontinued from the study at any time if the subject or the investigator feels that it is not in the subject's best interest to continue. The following is a list of possible reasons the subjects will be **dropped out** from the study:

- Stroke after surgery
- Perioperative myocardial infarction based on type 5 myocardial infarct criteria
- Haemorrhage complications requiring repeat surgery
- Use of continuous veno-venous hemofiltration or haemodialysis after coronary artery bypass graft surgery
- Delayed sternal closure
- Aortic cross-clamp duration of > 120 minutes and/or cardiopulmonary bypass duration of >180 minutes

All subjects are free to withdraw from participation at any time, for any reason, specified or unspecified, and without prejudice. Reasonable attempts will be made by the investigator to provide a reason for subject withdrawals. The reason for the subject's withdrawal from the study will be specified in the subject's source documents and the Case Report Form (CRF). If a subject is withdrawn from treatment due to an adverse event, the subject will be followed and treated by the investigator until the adverse event has resolved or stabilized.

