**Handling of Participant Withdrawals or Termination:**

Although subjects may withdraw from the study at any time and for any reason, (or may be withdrawn at the investigator's discretion), subject withdrawal should be avoided as much as reasonably possible. In any case, appropriate follow-up for withdrawals or termination. Subjects who are discontinued are not to be replaced. For subjects considered discontinued, the CRF must be completed up to the last visit performed.

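### Randomised, treated patients are to be dropped for six events during or after surgery, including perioperative MI, and no analysis set is defined, leaving the troponin comparison open to selection bias of unknown size

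*Combined protocol and SAP*

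**What the plan says.** The section Reasons for Withdrawal or Termination lists six grounds for dropping a subject: stroke, "Perioperative myocardial infarction based on type 5 myocardial infarct criteria", bleeding that needs reoperation, renal replacement therapy, delayed sternal closure, and "Aortic cross-clamp duration of > 120 minutes and/or cardiopulmonary bypass duration of >180 minutes". The Study Summary repeats the list (for example "Haemorrhage complications requiring repeat surgery"). A separate general clause reads "A subject may be discontinued from the study at any time if the subject or the investigator feels" that continuing is not in the subject's interest.

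Handling of Participant Withdrawals or Termination adds "Subjects who are discontinued are not to be replaced" and "For subjects considered discontinued, the CRF must be completed up to the last visit performed". It also says that "subject withdrawal should be avoided as much as reasonably possible". For withdrawals due to an adverse event, the protocol promises that "the subject will be followed and treated by the investigator until the adverse event has resolved or stabilized", without mentioning endpoint samples.

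Under Methods of Intervention, patients are randomised after consent, and the infusion runs for 24 hours from induction. Troponin I up to 48 hours after bypass and plasma glutamine at 24 hours are primary endpoints. The Statistical Analysis Plan covers randomisation, sample size and lists of endpoints. It names no analysis set, no method for missing data and no sensitivity analysis.

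**The concern.** All six grounds are post-randomisation events in patients already receiving study treatment. Infarction matters most. Goals of the Study uses troponin I as a measure of myocardial damage, and Expected Outcomes anticipates that glutamine protects the myocardium. On the investigators' own hypothesis there is no reason to expect infarction to be balanced between arms. Dropping those patients compares two groups selected on a consequence of the process under study.

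The direction of bias depends on the truth:

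- If glutamine prevents the events, more high-troponin controls leave and a real benefit is diluted.
- If glutamine raises event rates, harm is hidden in the endpoint comparison and a false benefit becomes possible. The event counts on the Research Sample Outcomes page of the case report form would still show the harm.
- If events and their severity are balanced, there is no bias.

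The data at risk are troponin at 6, 24 and 48 hours, the only glutamine sample after bypass, and later lactate and cardiac index. Clamp and bypass times are known by the end of bypass. For patients dropped on those grounds, the 5-minute samples and the atrial tissue taken then, which supplies four secondary endpoints, may be lost too. Ventilation, intensive-care and inotrope data can still come from the medical record. Blood not drawn on time cannot be recovered later.

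**Working it through.** **1. The plan's own figures.** Sample Size Justification uses a difference of 0.032 and an SD of 0.04 in the formula (0.0415 in the legend).

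- n per group = 2[(1.96 + 0.84) × 0.04 / 0.032]² = 2 × 3.5² = 24.5, so 25. This reproduces.
- 50 + 20% of 50 = 60. This reproduces.
- With SD 0.0415, d = 0.032/0.0415 = 0.771. Two-sided t-test power is 0.836 at 30 per arm, matching the stated 0.84, and 0.762 at 25 per arm.

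The section therefore points both ways: it adds 10 patients to cover drop-out, yet states power as if all 60 were analysed.

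The plan does not name the endpoint behind 0.032, so 0.77 SD is only a stand-in below. Event rates and correlations are assumptions.

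**2. True benefit, same severity threshold in both arms.** Let p be the share of controls dropped, c the (1−p) normal quantile, r the correlation between severity and outcome, and s the shift in severity under glutamine. Then

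retained difference = d + r[φ(c+s)/Φ(c+s) − φ(c)/Φ(c)].

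Example with p = 0.20, r = 0.5, s = d: c = 0.842, and 0.771 + 0.5 × (0.115 − 0.350) = 0.654, an attenuation of 15.2%.

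| Controls dropped | s = r × d, r = 0.3 / 0.5 | Attenuation | s = d, r = 0.3 / 0.5 | Attenuation |
|---|---|---|---|---|
| 5% | 0.760 / 0.743 | 1.5% / 3.7% | 0.745 / 0.728 | 3.4% / 5.6% |
| 10% | 0.753 / 0.726 | 2.3% / 5.9% | 0.727 / 0.698 | 5.7% / 9.4% |
| 20% | 0.745 / 0.702 | 3.4% / 9.0% | 0.701 / 0.654 | 9.1% / 15.2% |

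**3. No overall effect on the outcome, unequal drop-out.** Simulation with 30 per arm, 20,000 trials, overall means equal, and dropped patients 1 or 2 SD above retained ones:

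| Drop-out, glutamine v control | Type I error, 1 SD | Type I error, 2 SD |
|---|---|---|
| 30% v 10% | 0.104 | 0.270 |
| 15% v 5% | 0.064 | 0.109 |

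In the 2 SD cases nearly all false positives favour glutamine. Equal 10% drop-out, or analysing all 60, stays at about 0.05. A latent-threshold version gave 0.095 or 0.243 at 30% v 10%, and 0.062 or 0.104 at 15% v 5%.

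Equal overall means carry a condition: retained glutamine patients must sit lower than retained controls by the drop-out difference times the gap. That is 0.2 × 1 to 0.2 × 2 = 0.2 to 0.4 SD at 30% v 10%, and 0.1 to 0.2 SD at 15% v 5%.

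**4. Glutamine changes only the event rate.** With a 10-percentage-point change and events 2 to 3 SD higher, the all-randomised difference is 0.10 × 2 = 0.2 to 0.10 × 3 = 0.3 SD, in either direction. After removal it is 0, and the test rejects at about 0.05. A real effect disappears.

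**5. Price of keeping everyone.** Suppose 10% of each arm are complicated cases 2 or 3 SD higher. Simulated t-test power is:

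| Analysis | +2 SD | +3 SD |
|---|---|---|
| All 60 | 0.709 | 0.592 |
| Exactly those cases removed | 0.786 | 0.790 |
| 3 per arm removed at random | 0.663 | 0.547 |

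In this scenario 80% power needs about 37 (+2 SD) to 49 (+3 SD) analysed per arm.

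**The case against.** The strongest reply is that the protocol calls its list possible reasons for leaving the study and never says these patients leave the analysis. It also discourages withdrawal and has an unfinished sentence about appropriate follow-up. That stands as far as it goes: exclusion is an inference. But none of this wording commits to endpoint sampling or to inclusion in the analysis, while the case report form rule and the drop-out allowance point the other way.

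Second, the criteria are fixed in advance and the clinical team and analysts are blinded. This largely guards against choosing whom to drop by arm. It does not guard against selection through a treatment effect on the events themselves. The mechanism is clearest for infarction; the documents do not link clamp time or delayed sternal closure to glutamine.

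Third, the inflated type I error in step 3 needs an offset: more events under glutamine, but lower troponin in everyone else. That is correct, and the 0.10 to 0.27 range should be read with it. Without the offset there is no false benefit, but the harm is masked, as step 4 shows.

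Fourth, under the investigators' own hypothesis the bias is conservative and mostly modest. That also stands. It does not justify the rule, because the trial is meant to test that hypothesis.

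**Conclusion.** The concern holds and should be settled before enrolment, or at the latest before unblinding. Followed as written, the drop-out rule conditions a primary endpoint on perioperative infarction, and nothing in the analysis plan prevents the affected patients from being left out.

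Neither direction nor size can be determined from the documents. Under the stated assumptions the range runs from no bias (balanced events), through 1.5% to 15.2% dilution of a true 0.77 SD effect and complete loss of a 0.2 to 0.3 SD difference, to type I error of 0.10 to 0.27 in the offset scenario at 30% v 10% drop-out. The conclusion rests on validity and on data that cannot be recovered, not on any one of these figures. Confidence is medium, because exclusion from the analysis is inferred and event rates are unknown.

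**What to change.** 1. State that the primary analysis set is all randomised patients in the group assigned, using all available samples.
2. Separate ending participation from exclusion from analysis. The six events do not remove a patient from the analysis. Scheduled endpoint sampling and record retrieval continue unless consent is withdrawn or the investigator judges further sampling not to be in the patient's interest. Whether the infusion continues after an event is a clinical matter and is not addressed here.
3. Report the six events, deaths and missing samples by arm, from the Research Sample Outcomes page and the sampling records. State how missing samples are handled, since the all-60 figures above assume complete data.
4. Keep the analysis without the six-event patients only as a labelled sensitivity analysis.

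The cost is protocol and analysis-plan wording, the ethics review that the protocol requires for any amendment, and completing in the affected patients the sampling already scheduled to 48 hours. The downside is higher outcome variance: in the scenario of step 5, power with all 60 is about 0.71 to 0.59, against about 0.79 if exactly the complicated cases were removed. The stated power should be rechecked on that basis.
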